The overarching goal of the proposed study will be to replicate and extend these very encouraging initial findings by 1) increasing the dose of RET (3 vs. 2 sessions) so as to bolster treatment effects, 2) employing fMRI methods to identify patterns of brain activity (BOLD signal changes in regions of interest, ROIs, and functional connectivity) uniquely associated with R-E training and potentially predictive of treatment outcome, and 3) extending follow-up period to more completely assess the long-term effects of RET. Two groups of treatment-seeking smokers will remain abstinent overnight prior to undergoing a baseline cue reactivity assessment and fMRI session (only a portion of each group will undergo fMRI pre- and post-treatment. On their target-quit day, a three-day intervention phase will begin. On each day, Group R-E will receive RET whereas Group NR-E will first be administered retrieval cues that do not contain smoking content (NR) and then receive extinction training (E). The next day, all groups will undergo a cue reactivity assessment and fMRI session identical to baseline. This will end a four-day period of compensated abstinence designed to limit the possibility of reinforcing smoking memories via nicotine administration. Both groups will monitor their smoking behavior and undergo identical laboratory test sessions over a 6-month follow-up period. The aims/hypotheses are:

**Aim 1:** Assess the acute and long-term effects of R-E training on indices of smoking behavior/relapse.

**H1)** Relative to control, Group R-E will show decreased smoking (CPD) during follow-up.

**Secondary H1)** Relative to control, more participants in Group R-E will achieve a 60% smoking reduction (from baseline) during follow-up.

**Aim 2:** Assess RET effects (vs. baseline/control) on fronto-limbic-striatal circuitry function & behavior.

**H2.a)** Cue reactivity: Group R-E will evidence attenuated CR BOLD in medial prefrontal cortex (mPFC: dorsal anterior cingulate-dACC; ventromedial: vmPFC), limbic regions (amygdala, hippocampus) and ventral striatum. Greater reduction in BOLD response in regions of interest will predict decreased smoking.

**H2.b):** Group R-E will evince strengthened resting-state functional connectivity (rsFC) between mPFC regions and ventral striatum (frontostriatal circuits), reduced rsFC between mPFC and amygdala (frontolimbic); and the relative magnitude of change in rsFC will be inversely related to craving and smoking (e.g., CPD).

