**Fig. 5**

34/group) will receive a second CR assessment in the fMRI scanner whereas the remaining participants (n=98; 49/group) will receive the equivalent CR experience except in the CR lab. Participants will be required to remain overnight abstinent (CO verified) for the baseline CR session; monetary incentives will reinforce compliance with abstinence. This abstinence requirement ensures that baseline data will be collected under the same conditions of abstinence that will prevail for the subsequent four sessions (3 intervention and 1, 24-hr. test). Following the baseline CR assessment, participants will plan their cessation attempt to begin the night before the first of four consecutive daily laboratory sessions (Days 2, 3, 4 & 5 in **Fig. 5**), again with monetary incentives for abstinence throughout (**Fig. 5** under compensated abstinence). The purpose of abstinence during these four sessions is to minimize the likelihood of strengthening smoking memories with nicotine reinforcement via at-home smoking. Group R-E will then undergo 3 daily sessions of RET consisting of 5-min 'retrieval' smoking video followed 10 minutes later by 1-hour of 'extinction' training consisting of four sequences of smoking-related cues (same as in R21). The first test session will be performed 24-hrs after completion of the third RET session; it will be identical to the baseline CR session (i.e., a participant that received lab-based CR followed by fMRI CR at baseline, will receive the same arrangement in the 24-hr. test) with the exception that the lab-based CR will be assessed to both familiar (as in baseline session) and novel smoking cues. The conclusion of the 24-hr. test session also marks the end of compensated abstinence. Follow-up (lab-based cue reactivity) test sessions will occur at the following time points: 2-weeks, 1-month, 6-weeks, 2-months, 3-months, and 6-months. All test sessions will involve assessment of CR to both familiar and novel smoking cues. Participants will use smoking diaries to record daily smoking behavior throughout the follow-up period. A 'no-retrieval' control group, Group NR-E, will receive the same treatment as above except the 'retrieval' video will contain neutral, not smoking content. Both groups will be treated identically beginning with the 24-hr test session through study completion. All follow-up test sessions (**Fig. 5**, last box) will be identical to the first (24-hr) test session except (a) there will be no compensation for abstinence, (b) there will be no fMRI lab session, (c) participants will use diaries to collect daily information about smoking and craving, and (d) salivary cotinine will be collected to permit biochemical verification of self-report smoking/abstinence.

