
**ii. Participants:** A total of 166 treatment-seeking men and women smokers (83 per group), **aged 25 to 65**, will be enrolled. While we recruited smokers between the age of 21-65 in the R21, we have narrowed the age range in the proposed study in the interest of mitigating concern about the potential confounding effects of brain development in younger participants. Also, since more than 80% of smokers begin smoking before age 21, employment of this age range will ensure, even at the lower bound, that we are recruiting smokers with sufficiently long smoking histories to have well-established smoking-related memories. This age range also ensures the findings will be generalizable to the vast majority of smokers. Additional inclusion requirements are: a) smoke 10+ cigarettes/day for three or more years, b) be willing to make a cessation attempt, c) remain overnight abstinence prior to the baseline smoking cue reactivity assessment, and d) agree to comply with the reinforced abstinence regimen in place during the four laboratory sessions (3 intervention & 1 test). Prospective participants will be excluded if they meet DSM criteria for a psychotic disorder, severe major depression, bipolar affective disorder, substance dependence (other than nicotine) or have a neurological disorder/injury (e.g., dementia, brain tumor, Parkinson's disease, head injury).

**iii. Sample Size Estimation.** A sample of 166 participants assigned equally to 2 treatment groups will provide 80% power to detect clinically relevant reductions in smoking behavior while optimizing power ( $\geq 80\%$ ) to detect meaningful effects across the remaining hypotheses. Hypothesis 1a: In the R21 analysis, a greater reduction in CPD was seen in Group R-E as compared to Group NR-E (**Fig. 2b**: Cohen's  $d=0.5$ ). Since small studies are more likely to report larger effects than larger trials, we have designed this study to have at least 80% power to detect an effect of treatment on CPD with a 10% reduction from that observed in the R21 ( $d=0.45$ ). In the proposed study, we will measure CPD at each of 6 follow-up time points (**Fig. 6**). Under the assumption of independent observations, a total sample size of 78 participants randomized to each group will provide 80% power ( $\alpha < .05$ ) to detect an effect size of  $d=0.45$  between Group R-

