
Lastly, study staff will randomize participants to treatment group and fMRI condition. Participants will be randomized to the Group R-E or NR-E in a 1:1 allocation. Randomization will be done using a stratified random block design; randomization blocks will vary in size (3, 6 and 9) and randomization will be stratified across gender and baseline nicotine dependency (FTND score ≤ 5 vs. > 5). Relevant data from the clinical assessment will be used to assign participants to the corresponding randomization strata; then randomized within the current block of the strata. Following treatment randomization, participants will be randomized to receive fMRI or no fMRI in a 1:1 allocation (within each treatment strata) until 34 participants in each treatment assignment (68 total) have been successfully randomized to the fMRI protocol. This approach to randomization should mitigate accidental bias and produce comparable groups across possible confounds.

**viii. Baseline Cue Reactivity/fMRI Assessment:** The baseline CR session will be administered at one of our two identical lab locations (ABRL or TRAIN). Upon arrival, participants will undergo a smoking abstinence assessment involving self-report verification followed by breath CO assessment. Per recent study guidelines, participants will be considered overnight abstinent if their breath CO level is ≤ 10 ppm. Abstinence from alcohol/other drug use will be

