Validity and data integrity will be checked on an ongoing basis through the use of data audits. Study statisticians ([name]/[name]) will supervise quarterly data quality assessments (i.e., examination of the outcomes database(s) for missing data, unexpected distributions or responses, and outliers) performed by the study research staff. Accuracy and completeness of the data collected will be ensured by weekly review. A 10% random sample of the primary source document will be crosschecked with the database on a quarterly basis. If inaccuracies exceed 2%, then a second 10% will be randomly chosen for audit. Should data discrepancies be discovered, they will be resolved using original source documents. The REDCap system does not accept outliers, illogical response patterns, etc. The PI will have weekly meetings with the research staff to discuss qualitative comments received during data collection and any problems in data collection or entry. The statistician will periodically examine the database to look for irregularities. Initial data analyses will examine distributions of variable scores and comparability of baseline characteristics across conditions in case analyses need to be adjusted for these.

**fMRI Analysis Plan.** The hypothesis for 2a (CR) is that Group R-E will evidence attenuated CR in medial prefrontal cortex (mPFC: dorsal anterior cingulate-dACC; ventromedial: vmPFC), limbic regions (amygdala, hippocampus) and ventral striatum. Greater reduction in BOLD response in regions of interest will predict decreased smoking. fMRI data will be preprocessed using recommended procedures in SPM8 and as done previously. At the 1st-level, data will be analyzed using the GLM; events of interest (Smoking, Neutral) will be modeled as a boxcar canonically convolved hemodynamic response function, and HR and motion parameters entered as nuisance covariates. At the 2nd-level, 2 (Time: Pre, Post) x 2 (Group: R-E, NR-E) ANOVA will be used within an *a priori* ROI mask (amygdala, hippocampus, mPFC, ventral striatum;  $p < .05$ , pFWE). **Hypothesis for 2b (rsFC)** is that group R-E will evidence strengthened rsFC in frontostriatal circuitry; weakened rsFC in frontolimbic circuitry and the magnitude of rsFC will be inversely related to craving and smoking (e.g., CPD). **fMRI data analysis plan.** Similar to our previous work along with in scanner heart-rate and respiration entered as covariates, rsFC will

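### Blocks of 3 and 9 cannot give the stated 1:1 two-arm allocation and no odd-slot rule is stated; Section 12.0 also plans a comparison with a second control group that does not exist

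*Combined protocol and SAP*

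**What the plan says.** Section 10.0 vii (Clinical Assessment and Randomization) states "Participants will be randomized to the Group R-E or NR-E in a 1:1 allocation". The next sentence describes a stratified block design in which "randomization blocks will vary in size (3, 6 and 9". The strata are gender and FTND score (at most 5 versus above 5), which makes four. The same paragraph says "study staff will randomize participants to treatment group and fMRI condition". Equal arms are the intent elsewhere too: Section 10.0 ii has "A total of 166 treatment-seeking men and women smokers (83 per group" and Section 10.0 iii has "A sample of 166 participants assigned equally to 2 treatment groups".

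Only one comparator is defined. H1 in Section 1.0 reads "Relative to control, Group R-E will show decreased smoking (CPD) during follow-up", the Design Overview in Section 10.0 i says "A 'no-retrieval' control group, Group NR-E, will receive the same treatment as above", and the fMRI analysis in Section 12.0 is a "2 (Time: Pre, Post) x 2 (Group: R-E, NR-E) ANOVA".

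Four other places assume more than one control. The power statement for Secondary Hypothesis 1b (Section 10.0 iii) refers to controls in the plural. The Intervention section (10.0 ix) counts three groups. The Aim 1 hypothesis in Section 12.0 names two controls. The list of other secondary analyses in Section 12.0 includes a comparison of the controls with one another.

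**The concern.** A permuted block holds the allocation ratio only if its size is a multiple of the number of arms at 1:1. Two of the three sizes are not. Whoever builds the list must decide how to fill the odd slot: always the same arm, at random, or alternating. The plan records no such decision. The choices differ in the balance they deliver, and one of them would break the stated 1:1 ratio. A later reader could not tell from the plan whether the schedule was built as intended.

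The second matter is separate. An analysis between control groups needs at least two of them, and the design has one. The analysis section also words its leading hypothesis around a comparator that does not exist.

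**Working it through.** **The plan's own figures.** With d = 0.45, power 80% and alpha 0.05 (two-sided assumed, because sidedness is not stated for cigarettes per day), n per group = 2(1.960 + 0.842)² / 0.45² = 77.5, so 78, as Section 10.0 iii states. Taking the plan's repeated-measures figure of 62 as given, 62 / (1 − 0.25) = 82.7, so 83 per group and 166 in total, also as stated. These are two-arm numbers.

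**Divisibility.** Slots per arm are 3/2 = 1.5, 6/2 = 3 and 9/2 = 4.5. Only the 6 works; the nearest splits for the others are 2:1 and 5:4. All three sizes divide by 3 (1, 2 and 3 per arm), which would suit a three-arm 1:1:1 design.

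**If the odd slot always went to one arm.** With the three sizes equally likely, that arm's expected share is (2 + 3 + 5)/(3 + 6 + 9) = 10/18 = 55.6%, and 166 × 10/18 = 92.2, or about 92:74. This is an upper bound and would itself contradict the 1:1 statement.

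**Simulation.** 8,000 schedules per scenario, N = 166, four strata, block sizes equally likely, last block in each stratum truncated. The documents give no stratum sizes, so three splits were assumed: 42/42/41/41; 30/30/53/53 (36% women as in Section 5.0, FTND halves); and 18/42/32/74. Ranges below cover the three splits.

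| Scheme | 95% range in R-E | Mean absolute arm difference | 95th percentile | Difference ≤ 4 | Mean worst-stratum difference |
|---|---|---|---|---|---|
| 3/6/9, odd slot randomised | 78–88 | 3.8 | 10 | 70% | 3.5–3.6 |
| 3/6/9, odd slot alternated within stratum | 81–85 | 1.8–1.9 | 4 | 95–96% | 1.8 |
| 4/6/8 | 81–85 | 1.6–1.7 | 4 | 98% | 1.5–1.6 |
| Simple randomisation | – | 10.3 | 26 | 30% | – |

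**Predictability.** The share of assignments fully determined, if block size and earlier assignments are known, is 13% for 3/6/9 with a randomised odd slot, 24% for 4/6/8, 27% for 4/6 and 31% for 2/4/6. For 3/6/9 with alternation it is 13% if the favoured side is unknown and up to about 24% if it is known.

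**Power and efficiency.** For a two-sided t-test at d = 0.45 on all 166:

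- 83:83: power 82.2%
- 88:78: power 82.0%, relative efficiency 4 × 88 × 78 / 166² = 0.996
- 92:74: power 81.7%, relative efficiency 4 × 92 × 74 / 166² = 0.988

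**Control groups.** Sections 1.0, 10.0 i, 10.0 vii and the fMRI plan in 12.0 agree on two groups, R-E and NR-E. No section defines a further control, so the between-controls analysis has nothing to compare.

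**The case against.** The strongest reply is that this is a clarification with no inferential cost. Under the one reading that respects 1:1, assignment stays random, the ratio holds in expectation, power changes by 0.2 percentage points, and blocks of 3, 6 and 9 still give much better balance than simple randomisation. Stratification is unaffected, and Section 12.0 allows characteristics that are imbalanced at baseline to be considered as covariates. Odd blocks can also be deliberate: with a randomised odd slot they are less predictable than even blocks. A stated alternation rule nearly matches 4/6/8 on balance, so even blocks are not the only remedy. The control-group wording is a separate editorial matter, and H1 already makes the Aim 1 contrast clear.

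Most of this stands. There is no bias or power problem here, 92:74 describes a departure from the plan rather than the plan, and documenting a symmetric odd-slot rule is an acceptable alternative. The t-test figures show only that the change is negligible; they are not the power of the planned longitudinal model. None of this supplies the missing rule, and the comparison between control groups still cannot be carried out.

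**Conclusion.** The point holds. The block sizes are incompatible with an exact 1:1 split in two of three cases, and the plan leaves the odd slot undecided. The practical effect is small. With a randomised odd slot the mean arm difference is 3.8 rather than about 1.6 with blocks of 4, 6 and 8, its 95th percentile is 10 rather than 4, and power is essentially unchanged. What is lost is part of the balance that blocking is meant to give, and the ability to reproduce or audit the rule. The between-controls analysis in Section 12.0 cannot be run.

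The divisibility argument and the missing second control rest on the text alone. The imbalance figures rest on assumed stratum sizes and equally likely block sizes, and barely change across the three splits tried. A leftover from a three-arm design would explain both defects, but the documents do not show it. The list actually used is not in the documents, so nothing here says that the implemented allocation was unequal.

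**What to change.** In Section 10.0 vii, replace 3, 6 and 9 with even block sizes within the four strata, for example 4, 6 and 8, and avoid blocks of 2. The cost is more predictable assignments than with a randomised odd slot (24% against 13% in the worst case), so conceal the block sizes from the study staff who randomise.

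If a list is already in use, check it first. If its odd slots were randomised or balanced between arms, write that rule into the section and leave the list alone. If they always favoured one arm, use even blocks for the remaining schedule.

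Separately, restate the Aim 1 hypothesis in Section 12.0 as R-E versus NR-E, delete the between-controls item from the other secondary analyses, and correct the group wording in Sections 10.0 iii (Secondary Hypothesis 1b) and 10.0 ix.

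The total cost is one sentence on blocking, a check of any existing list, and four text edits, with no added participants or procedures.

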assessed via breathalyzer and urine drug screen (UDS). Failure to meet abstinence requirements will result in rescheduling. Following the abstinence assessment, participants will be seated comfortably in front of a computer monitor and have the HR and SC sensors and BP cuff affixed as described above. They will remain seated comfortably for 10 min, after which 50-sec of continuous HR and SC data will be collected; next the participant will complete the CQ, MF and have their BP assessed. Having completed pre-cue assessments, the participant will remain seated for 5-min; they will then view the smoking-related video described above. Continuous HR and SC will be collected during the first 50-sec of the video whereas the CQ, MF and BP will be collected immediately after viewing the video. Following a break, participants randomized to the fMRI condition will be escorted to the fMRI suite. Participants will practice the experimental task while inside a mock scanner in order to reduce scan-related anxiety and enhance data integrity. Next, participants will be administered the fMRI procedures. In brief, we will collect a hi-res MPRAGE structural image, followed by 6-minute eyes-closed resting-state sequence and then participants will be scanned while performing a smoking CR task (8 ½ min duration) that involves viewing alternating blocks of neutral cues (e.g. pencil: 40 sec), fixation and craving ratings (30 sec) and smoking cues (e.g. cigarette: 40 sec). Participants not randomized to the fMRI condition will remain in the CR laboratory and receive the same CR regimen as administered in the fMRI condition. This ensures that all participants have equivalent stimulus exposure.

At the completion of the baseline CR/fMRI assessment, participants will schedule their next visit with study staff, and they will be reminded that their quit attempt will begin the night before and that it will be the first of four consecutive daily visits for which they will receive abstinence-based compensation. The rationale for implementing a reinforced abstinence procedure was to ensure that extra-study smoking (e.g., at home) does not interfere with any effects of treatment (RET or otherwise) or the treatment effects assessed in the initial 24-hr test session. Lastly, participants will receive compensation.

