## 12.0 Data Management

Baseline demographic and clinical measures will be compared across groups using standard statistical methods (e.g., Chi square test of independence for categorical variables; Univariate ANOVA for continuous variables). Characteristics that (i) display imbalance at baseline, (ii) are associated with a dependent measure, or (iii) are known to be predictive of study outcomes (e.g., craving, smoking) will be assessed for inclusion as covariates in the final models. **Primary Aims Analysis:** The primary hypothesis of Aim 1 is that Group R-E will evidence decreased smoking behavior during follow relative to both control groups. Smoking behavior will be measured via smoking diary/TLFB recovered at each visit or by phone, from which, the mean CPD will be calculated between each visit for the period until the last attended visit. Additionally, the smoking diary/TLFB data will be used to compute an indicator of those that achieved a  $\geq$ 60% reduction in CPD relative to baseline smoking at each visit. Generalized linear mixed effects models will be used to analyze the longitudinal smoking behavior data during follow up (using appropriate

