distributions). Overall statistical significance for the effects of treatment group, time, and their interaction will be assessed using a likelihood ratio test that compares the final model to a model consisting of an intercept term alone. The pre-specified hypothesis will be tested using model-based estimates to construct group comparisons across all the planned time points. Normality of residuals will be tested for models where appropriate and when found in error, appropriate transformations or non-parametric methods will be employed. Although mixed effects models have been proven highly efficient in cases where follow up data is missing at random, to accommodate other types of missing data, we will perform analyses using multiple imputation methods (Bayesian approach using both MCMC and FCS). The primary hypothesis associated with Aim 3 is that Group R-E will evidence decreased cue-elicited craving during follow-up testing. General linear mixed effects models will be constructed to assess group differences in craving over time. **Secondary Analysis:** Smoking relapse (i.e., days to 3 consecutive days of smoking ≥5 cigarettes) will be tested using a Cox Proportional Hazards regression model. Log-Log plots of the survival function and inclusion of a time variable treatment term will assess the proportionality assumptions and if models fail this assumption, a stratified Cox Regression model will be used. Also, we will measure end of study 7-day point prevalence abstinence as well as continuous abstinence using smoking diary/TLFB data. The effect of R-E training on abstinence outcomes will be tested using logistic regression models. **Biological Variables:** Exploratory analysis of sex effects on study outcomes will be assessed through main effects and the interaction between sex and study treatment assignment. Where significant interactions are found, sex stratified analyses will be conducted to assess the role of sex in the effect of RET on study outcomes. **Other secondary analyses** will assess i) differences between the control groups on main outcomes, ii) craving and cue reactivity differences during the three intervention sessions, and iii) the effects of treatment on ambient or background craving and cue reactivity (i.e., non-cue-elicited outcomes obtained early in test sessions). All analysis will be conducted using SAS/STAT v. 9.4 and Stata v. 14.

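### Allocation is stratified by gender and FTND, but no primary or secondary model commits to these factors; if they are prognostic, the linear CPD and craving tests are conservative and lose some power

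*Combined protocol and SAP*

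**What the plan says.** Section 10.0, item vii sets the allocation: "Participants will be randomized to the Group R-E or NR-E in a 1:1 allocation", in blocks, and "randomization will be stratified across gender and baseline nicotine dependency", with FTND cut at 5. A second step follows: "participants will be randomized to receive fMRI or no fMRI in a 1:1 allocation", until 34 people in each arm are assigned to scanning.

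Section 12.0 describes the CPD and 60%-reduction analyses as generalized linear mixed models with effects of arm, time and their interaction. Craving has a general linear mixed model, relapse a Cox model and abstinence a logistic model. None of these descriptions names gender or FTND stratum. The stratified Cox model is a fallback for non-proportional hazards, and no stratifying variable is given for it.

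Two passages in Section 12.0 bear on the gap. Baseline characteristics that are imbalanced, are associated with a dependent measure, or "are known to be predictive of study outcomes (e.g., craving, smoking) will be assessed for inclusion as covariates in the final models". And for sex: "Exploratory analysis of sex effects on study outcomes will be assessed through main effects and the interaction between sex and study treatment assignment".

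**The concern.** A stratified design forces the arms to be alike on the strata. This removes the strata's contribution from the random variation in the treatment contrast. If the strata predict the outcome and the model omits them, that variance stays in the model's error term. The reported standard error then exceeds the true one, confidence intervals are too wide, and the test rejects less often than its nominal 5%. Some of the precision gained by stratifying is not used.

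The covariate screen does not close the gap. Its imbalance criterion is unlikely to select factors that the design balances. Its association criterion is decided after looking at outcome data. Its known-predictor criterion could admit either factor, but the plan gives no list or threshold and promises only an assessment. The content of the primary model on this point is therefore open until the data are in.

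**Working it through.** **Inputs from the documents.** From Section 10.0, item iii, for CPD: d = 0.45, alpha 0.05, 80% power, six follow-up visits, AR(1) correlation 0.9, 62 per group before dropout, 25% dropout. Sidedness is not stated for CPD, but two-sided reproduces the plan's 78. From Section 5.0: 36% women.

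**Assumptions.** The documents do not give R2, the share of between-person variance in the time-averaged outcome that gender and FTND explain. I take 0 to 0.20. CPD is treated on a linear scale and d is taken on the total SD.

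**Step 1: reproduce the plan's sample size.**
- Independent observations: n = 2 × ((1.960 + 0.842)/0.45)² = 77.5, so 78 per group, as stated.
- The variance of the mean of AR(1) repeats at 0.9 is 0.8239 for six visits and 0.7978 for seven. Then 77.5 × 0.8239 = 63.9 (64 per group) and 77.5 × 0.7978 = 61.8 (62 per group). The stated 62 is matched with seven occasions and is within two with six.
- Dropout: 62/0.75 = 82.7, so 83, as stated.

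**Step 2: baseline.** With 62 per arm and six visits, SE = sqrt(0.8239 × 2/62) = 0.163 and d/SE = 2.760. Power = Φ(2.760 − 1.960) = Φ(0.800) = 78.8%.

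**Step 3: effect of omitting the strata.** With balanced strata, the true SE is the model SE times sqrt(1 − R2). So:
- SE overstatement = 1/sqrt(1 − R2)
- type I error without strata = 2Φ(−1.960/sqrt(1 − R2))
- power without strata = Φ(0.800/sqrt(1 − R2))
- power with strata = Φ(2.760/sqrt(1 − R2) − 1.960)

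For R2 = 0.10, sqrt(0.90) = 0.9487. The SE ratio is 1.054, type I error is 2Φ(−2.066) = 3.9%, power without strata is Φ(0.844) = 80.1%, and power with strata is Φ(0.949) = 82.9%.

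| R2 (assumed) | SE too large by | Type I error, strata omitted | Power, omitted | Power, included | Difference (points) |
|---|---|---|---|---|---|
| 0 | 0% | 5.0% | 78.8% | 78.8% | 0 |
| 0.05 | 2.6% | 4.4% | 79.4% | 80.8% | 1.4 |
| 0.10 | 5.4% | 3.9% | 80.1% | 82.9% | 2.8 |
| 0.20 | 11.8% | 2.8% | 81.5% | 87.0% | 5.5 |

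**Step 4: check by simulation.** I ran 4,000 trials per setting with 62 per arm on average, 36% women, an assumed 50/50 FTND split and equal contributions of the two factors to R2. Blocks were 2, 4 and 6, because the stated sizes 3 and 9 cannot be split evenly between two arms (a separate matter). At R2 of 0.05, 0.10 and 0.20, power without versus with strata was 79.0 vs 80.6%, 79.8 vs 82.6% and 80.5 vs 86.5%. Type I error without strata was 4.3, 4.2 and 2.7%; with strata it was 4.7, 5.3 and 4.7%. This agrees with the formulas within simulation error.

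The SE and type I columns depend only on R2, so they apply equally to the linear craving model. The power columns are specific to the CPD inputs.

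**The case against.** The strongest reply is that the plan already provides for this. If gender or FTND is prognostic, two of the three screening criteria put it up for inclusion; if neither is, nothing is lost. Sex is an obvious candidate, since Section 2.0 reports that the R21 CPD and craving results were adjusted for it. This part stands: a reader might infer that no analysis contains these factors, and that is too strong. Sex has an exploratory analysis, and the screen could admit either factor. But a factor that "will be assessed for inclusion as covariates in the final models" is not a pre-specified term, and a partly outcome-driven choice for the primary model is what pre-specification is meant to prevent.

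Other stronger readings are tempting, and the documents do not support them.
- **The trial falls short of its planned power.** With d on the total SD, power without the strata never drops below its R2 = 0 value of about 79%. The loss is against a better analysis. The R21 effect of 0.50 was itself covariate-adjusted, so an unadjusted analysis could face a smaller d if that figure used a residual SD. The documents do not say which SD was used.
- **fMRI assignment belongs in the models too.** It is a second randomisation after treatment allocation, not a stratification factor. Unscanned participants receive the same cue regimen: "This ensures that all participants have equivalent stimulus exposure". Nothing in the documents suggests that scanning affects smoking or craving.
- **Standard errors are inflated in every model.** The mechanism is a linear-model result. In logistic and Cox models, omission mainly attenuates the estimate. In the scanned subset, the wording leaves open whether scanning is allocated within arm only or within arm-by-stratum cells. If within arm only, the strata are not balanced there by design, so the argument from design balance does not apply.
- **False positives rise.** The departure goes the other way, below 5%.

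**Conclusion.** The point holds in a limited form. Allocation is stratified by gender and FTND, and no primary or secondary outcome model is committed to including them. In the linear CPD and craving models, the consequence is a conservative test and a standard error overstated by 0 to 11.8% for R2 between 0 and 0.20. For CPD, power is 0 to 5.5 points below the adjusted analysis.

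The size rests on an assumed R2 and is nil if the strata are not prognostic. It also takes the arms as balanced within strata at 62 completers each. Dropout would loosen that balance and bring the unadjusted type I error closer to 5%. If CPD is fitted with a non-linear link, the figures are a guide only. The validity of the trial is not threatened. This is avoidable imprecision, together with a primary model whose covariates are not fixed in advance.

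**What to change.** State in Section 12.0 that gender and FTND stratum (up to 5 versus above 5) are fixed effects in the CPD and craving mixed models, whatever the covariate screen shows. Include both also in the 60%-reduction, abstinence and Cox models, where the reason is attenuation rather than the standard error. Keep the covariate screen for sensitivity analyses. No fMRI-assignment term is needed on this ground.

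The cost is two degrees of freedom per model and a sentence or two of SAP text. Both variables are already collected before randomisation, so no new data are needed. If the strata turn out not to be prognostic, the adjustment costs almost nothing: in the simulation at R2 = 0, power was 78.4% both with and without them.
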